Patients will be asked to refrain from any additional treatments including pelvic floor physical therapy, or new prescriptions for intravaginal muscle relaxants or narcotic medications during the first month following the initial TPI. If patients are already taking muscle relaxants or narcotics, they will need to either remain stable or decrease the dosage and frequency of the medication. If patients are already receiving pelvic floor physical therapy, they may continue treatment. If patients require increased use of these medications or additional therapies due to worsening or uncontrolled symptoms, these treatments will be provided at the discretion of the treating clinician. These patients will then be evaluated as an intention to treat cohort. In addition, at the one month follow-up visit with the clinician, further treatments will be offered based on the patient's need for further symptom control.

We hope that the information obtained by this study will help guide clinicians to make an evidenced based decision on the clinical efficacy as well as cost effectiveness of two transvaginal trigger point injection protocols for patients with high-tone pelvic floor dysfunction.

Methodology

A randomized, double blind two arm study. Up to 40 women will be included to complete this study. We may enroll up to 60 patients to account for possible dropouts, with each arm having up to 20 subjects. This is a pilot trial and a formal sample size has not been completed. Subjects will be recruited by physician referral or word of mouth. Study activities will take place at the Women's Urology Center in the south tower of Beaumont Hospital, Royal Oak.

Screening

Subjects are eligible to participate in this study if they are a woman greater than 18 years old and have pain localized to the pelvis for greater than 3 months. Overall pelvic pain score must be greater than 4 on the VAS. They will be screened with assessment of last menstrual period (LMP) and a urine pregnancy test. If the woman has had a tubal ligation or a hysterectomy, the pregnancy test will be waived.

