A vaginal exam will be performed obtaining a pH and wet mount. If the woman has vaginitis on her wet mount at screening, she may be given a prescription for the appropriate medication per standard of care and be re-screened. She must wait at least 3 days after treatment and may be re-screened once. The vaginal exam will also include a levator exam and the patient must have the finding of high tone pelvic floor dysfunction. This will be determined by the clinician and is defined as diffuse spasms and pain with palpation of the levator complex. Pain scores from 0-10 on the VAS will be recorded according to positions on a clock as rated by the patient (Figure 1).

Page **4** of **14**

Informed consent will be obtained from women meeting the screening and inclusion criteria (see below).

Following screening, consent and enrollment, a complete medical history will be obtained and/or confirmed from a prior visit. The intake form will be the same history form that all patient's presenting to the Women's Urology Center are asked to fill out. Information obtained includes demographics, current and past medical conditions, surgical history, social history (smoking, drugs, education, caffeine use, and employment), current medications, and allergies. Past treatment history for pelvic pain including physical therapy, trigger point injections, hydrodistension, cystoscopy, and surgery will be recorded. Subjects in both groups will then be asked to fill out baseline questionnaires including pain score on the VAS and the BPI.

The woman will then be randomized to one of 2 treatment arms in a 1:1 pattern.

Proposed intervention, if applicable (e.g., study visits, surgical procedure, administration of drugs, etc.) or collection of data (e.g., survey, questionnaire, etc.).

Subject enrollment and treatment may both occur at the initial visit. If desired, these visits may also be scheduled as separate visits within a 7-14 day period of time.

The first arm (Group 1) will receive TPI with a steroid and a local anesthetic followed by saline and the second arm (Group 2) will receive a local anesthetic followed by a mixture of 200u of Onabotulinumtoxin A and saline. Each group will receive injections globally throughout the pelvic floor at 1, 3, 5, 7, 9, 11 o'clock (Figure 1). See below.

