Subjects may be permitted to withdraw from the study if they have poor resolution of their pain or worsening of their symptoms. If they feel that they need other therapy during the first 30 days that is not permitted by the study (additional physical therapy, higher or more frequent doses of vaginal valium or pain medications, repeat TPI, etc.) they may be withdrawn and will be evaluated by the clinician for other treatment options. Patients who withdraw from the study will be asked if they are willing to fill out post questionnaires. Either group can get additional therapy following the first 30 days following the TPI. Furthermore, either group may have repeat TPI with kenalog one month following the original injection but patients may not undergo TPI with onabotulinumtoxinA following the original injection unless they withdraw from the study and are unblinded to prevent overdose of onabotulinumtoxinA. If additional TPIs with kenalog and ropivicaine are indicated at any of the follow up visits, the injections will be prepared and administered in the Woman's Urology Center, per routine standard of care. In no way will their withdrawal from the study impact what treatments will be offered to them. Subjects may also withdraw from the study without any reason given. If they do not feel comfortable continuing treatment by the study clinicians or at the WUC, they will be referred to another provider/site not involved in the study.

Schedule of Activities

| | Initial Visit | Treatment Visit | 30 days | 90 days | 180 days |
|--|----------------------|--|----------------------------|----------------------------|----------------------------|
| | Screening Consent | Baseline Questionnaires and physical exam (May be done at initial visit) | | | |
| Screening | x | | | | |
| Consent | X | | | | |
| Intake medical history form | X | X (If not done at initial visit) | | | |
| Urine pregnancy test ^a | x | | | | |
| Q tip test | X | X | Xp | Xp | Xp |
| Vaginal pH and wet mount | X | X (As needed) | X ^b (As needed) | X ^b (As needed) | X ^b (As needed) |
| Assess concomitant meds | X | X | Х | X | X |
| Vaginal exam assessment for high tone pelvic floor dysfunction with record of patient reported levator pain scores | X | X | Xp | Xp | Xb |
| Vital signs | X | X | Xb | Xb | Xp |
| Total overall pelvic pain score on VAS | x | X (done pre and post TPI) | X | x | X |
| BPI | | X | x | X | X |
| Trigger point injection | | X | As needed | As needed | As needed |

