- Local anesthetic toxicity (numbing medication could be absorbed through the bloodstream into the rest of the body affecting your breathing, heartbeat, blood pressure)

There is a risk of an allergic reaction from any medication. Symptoms may include swelling, skin rash and/or headache, difficulty swallowing or talking, trouble breathing, muscle weakness. Symptoms can occur days to weeks after injection. There may be unknown side effects or problems that could result in serious illness or even death.

Inclusion Criteria

- Provide informed consent
- Healthy women \geq age 18 regardless of menopausal status
- Willing and able to fill out study questionnaires. In patients that are unable to read, the research nurse will be available to assist.
- High-tone pelvic floor dysfunction on vaginal exam
- A pelvic pain score of ≥ 4 on screening VAS
- Pain perceived to be in the pelvis that has been present for at least 3 months.

Exclusion Criteria

- Patients that have had Botox to the bladder within the last 8 months
- Patients that have had Botox outside the bladder of ≥ 160 u within the last 12 weeks.
- Patients that have had transvaginal trigger point injections of any form (Botox or steroid) in the last 3 months
- Pregnancy
- Concomitant use of any narcotic drug, alcohol, or any illicit drug use during the study period that could be deemed unsafe in combination with study medication as judged by the investigators.
- Any evidence of vaginitis on wet mount slide at initial visit that is untreated.
- Subject with any other vaginal epithelial disorder that could affect absorption of medication as deemed by the investigators.

Page **10** of **14**

- Any indication/condition/medication that the investigators identify as contraindicated in conjunction with study medication.
- Systolic blood pressure > 160 mm Hg on screening blood pressure
- Heart rate > 110 beats/minute on screening heart rate

Randomization

Subjects will be randomized to one of the two trigger point injection types by a sealed randomization envelopes (or similar randomization) created by our biostatistician. Patients will be randomized in a 1:1 pattern in varied randomized block design.

Recruitment

We anticipate recruitment will come from volunteers with pelvic pain both within and outside the Beaumont health care system urology and gynecology practices by physician referral and word of mouth.

Data Analysis

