This study is an exploratory pilot study. Descriptive statistics, which will be provided for all variables, will be the main focus of the analysis because of the small sample size. Descriptive statistics will consist of frequency tables and bar charts for categorical variables, as well as summary statistics tables and boxplots for continuous variables.

Exploratory data analysis will be conducted on the data, particularly focusing on comparisons between the two treatment groups. Formal significance testing will be done to analyze group differences in terms of the baseline variables and clinical characteristics at time of treatment.

Since both the VAS and the BPI scores are given on ordinal scales, the marginal distributions of each of these scores will be provided for both time of treatment and 30 days after. For each subject, the difference in their score from pre to post will be calculated. Frequencies will be tabulated for the number of subjects whose pain score improved the number whose pain score stayed the same, and the number whose pain score worsened. The proportion of subjects in these categories will be compared between groups. Bar graphs will be created to illustrate the distribution of this variable. Nonparametric tests may be used to compare groups based on the distribution of the outcome variables.

Data Safety Monitoring Plan

An independent physician (not connected with the study, but familiar with the use of trigger point injections) will review study records at the half-way point of enrollment for each arm of the study to ensure the safety of subjects and lack of significant adverse effects. As an on-going plan, any adverse effects (prolonged bleeding, hemodynamic changes, significant patient pain, or other deemed significant by clinicians) will be reported to the research nurse and then to the PI at the time of the event. Adverse events, serious adverse events, and unanticipated problems not listed in the risks section of this protocol will be reported per federal regulations and IRB guidelines.

Stipend

Participants will receive a check for \$15 from William Beaumont Hospital following each of the five study visits. A total stipend of \$75 will be paid to those who complete all study visits.

References:

- 1. Ortiz DD: Chronic pelvic pain in women. *American family physician* 77(11), 1535-1542 (2008).

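### When enrolment and injection are separate visits, the only scheduled pregnancy test can be up to 14 days old at injection, and no repeat is listed

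*Protocol*

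**What the plan says.** The protocol's section on the proposed intervention first permits a single visit: "Subject enrollment and treatment may both occur at the initial visit". It then offers an alternative: "If desired, these visits may also be scheduled as separate visits within a 7-14 day period of time".

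The Screening section deals with pregnancy once: "They will be screened with assessment of last menstrual period (LMP) and a urine pregnancy test". The test is waived after tubal ligation or hysterectomy. Pregnancy appears in the Exclusion Criteria without reference to any visit.

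In the Schedule of Activities the row reads "Urine pregnancy test ^a | x", with the mark under Initial Visit and an empty cell under Treatment Visit. Footnote a limits the test to premenopausal women who have had neither tubal ligation nor hysterectomy. Other rows are marked at both visits: levator exam, vital signs, concomitant medications, pH and wet mount (as needed at the treatment visit), and the overall pain score, "Total overall pelvic pain score on VAS | x | X (done pre and post TPI").

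**The concern.** The pregnancy exclusion is there to keep pregnant women from being given the study drugs, so what matters is her status on the day of injection. If the injection comes at a later visit, a negative result from the initial visit does not cover the days in between. A woman could follow the plan exactly, with every scheduled box ticked, and be injected without that exclusion having been verified at exposure. This is a participant-safety matter first. It also has a trial-conduct side: a pregnancy found after randomisation would cost a randomised woman in a pilot that aims for up to 20 per arm.

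**Working it through.** There is no planned figure to reproduce. The check is a comparison of visit timing with the Schedule.

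**Age of the pregnancy result at injection** = day of injection − day of test. The only scheduled test is on day 0, the initial visit.

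- Same-day route: 0 − 0 = 0 days.
- Split route: the window ends at 14 days, so the largest value is 14 − 0 = 14 days. If the window is read as starting at 7 days, the smallest is 7 − 0 = 7 days.

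**What is rechecked at a separate treatment visit**

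| Item bearing on eligibility | Initial visit | Treatment visit |
|---|---|---|
| Overall VAS | yes | yes, before and after injection |
| Levator exam for high tone | yes | yes (also in the injection procedure) |
| Vital signs | yes | yes |
| Concomitant medications | yes | yes |
| pH and wet mount | yes | as needed |
| Urine pregnancy test | yes | not listed |

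**Could other text close the gap?** The Screening section mentions one test. The injection procedure describes the levator exam and pain scores before injection, but no pregnancy test. The Inclusion and Exclusion Criteria contain no contraception requirement. Nothing elsewhere supplies a repeat.

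**When does randomisation happen?** The protocol places it after the baseline questionnaires. The Schedule's column heading allows these at the initial visit. The visit at which a split-visit woman is randomised is therefore not fixed. If it is the initial visit, a positive test on the treatment day would remove a woman who is already randomised. A repeat test therefore needs a stated order.

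**How many women?** The result is old only for women who are both in footnote a and on the split route. The documents give neither share. The count runs from 0, if every woman is treated on the day of enrolment, to all footnote-a women among the up to 60 who may be enrolled. This counts women with an older result, not pregnancies; the documents offer no basis for estimating the latter.

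**The case against.** The strongest reply is that the split route is optional, that pregnancy is listed as an exclusion without tying it to screening, and that the protocol sets no validity period for the test. A clinician who knew of a pregnancy on the injection day would still have to exclude the woman, and a result 7 to 14 days old is not declared invalid anywhere. This limits the point but does not remove it: the exclusion applies, yet the plan schedules nothing that would reveal a new pregnancy, while it does schedule repeats of most other checks.

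Two stronger readings are tempting and are not supported.

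*Eligibility is checked only at the initial visit.* The Schedule contradicts this, as tabulated above. No text says what follows if a repeated value no longer meets an entry criterion, but the measurements themselves are taken.

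*The VAS threshold should be reapplied to the pre-injection score.* The inclusion criterion is worded on the screening score: "A pelvic pain score of ≥ 4 on screening VAS". A reader might infer that women whose pain has eased by the treatment day spoil the comparison. To gauge this, assume normal scores rounded to 0–10, SD 2, pre-selection mean 5 to 6 and between-visit correlation 0.6 to 0.8; none of these is in the documents.

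- Of women scoring at least 4 at screening, 5% to 14% would then score below 4 on the treatment day: 0.05 × 40 = 2 to 0.14 × 40 = 5.6 of 40 if every visit were split, and none if all were same-day.
- Those women would average about 2.5 to 2.8, with under 2% at 0, so nearly all could still improve.
- Randomisation makes them equally likely in either arm, so no between-arm bias is expected; at most some sensitivity is lost.
- Reapplying the cut has its own cost. With the same correlation between all visits and no treatment effect, selecting on screening alone gives a mean later change of about 0. Selecting on the analysed baseline as well gives about −0.06 to −0.25 points, through regression to the mean.

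**Conclusion.** The point holds for the pregnancy test and only on the split-visit route. Followed as written, the plan lets the pregnancy exclusion rest on a result up to 14 days old at injection, against 0 days on the same-day route, and gives no reason for the difference. This conclusion needs no assumption beyond the protocol's own visit window and Schedule. How many women it touches is unknown and may be none.

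The VAS does not support a second eligibility finding. What remains there is a matter of wording. The Screening section says "Overall pelvic pain score must be greater than 4 on the VAS", whereas the inclusion list admits a score of exactly 4. The protocol's Data Analysis section reports scores at the time of treatment ("the marginal distributions of each of these scores will be provided for both time of treatment and 30 days after"), while the SAP refers only to baseline. Because the overall VAS is recorded at both the initial and the treatment visit, a split-visit woman has two candidate baselines.

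**What to change.** 1. In the Schedule of Activities, add the urine pregnancy test to the Treatment Visit column for the women in footnote a when the visits are separate, with the result available before injection. This verifies an existing exclusion and leaves the treatment itself unchanged.
2. State that, on the split route, randomisation follows this check, so that no randomised woman is excluded by it.
3. Reconcile the two VAS entry thresholds (>4 in Screening, ≥4 in the Inclusion Criteria), and state in both protocol and SAP which VAS is the analysed baseline. Do not add a second VAS cut at the treatment visit.

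The cost is one Schedule cell, a few sentences, one urine strip per applicable split-visit woman, and an occasional replacement before randomisation. The SAP, dated December 2018, is written in the past tense. If enrolment has closed, what can still be done is to report how many women had separate visits and the interval from test to injection.

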Intralevator trigger point injections will then be performed as follows: With the subject in lithotomy position and blinded by a drape, the clinician will perform a pelvic exam to palpate the muscles of the levator complex. Pain scores from 0-10 on the VAS will be recorded according to positions on a clock as rated by the patient. The pharmacy will provide the injection medications in dark syringes in the following solutions: For patients randomized to group 1, a mixture of 40mg/1 ml of triamcinolone (40 mg) and 29cc of ropivicaine 0.5% (5cc/6 sites) will be used first followed by 6 cc of saline (1cc/injection site). In Group 2, patients will receive an injection of 30 cc of ropivicaine (5cc/6 sites) followed by a mixture of 200 u of onabotulinumtoxinA and 6cc of saline. In patients weighing less than 58kg, the ropivicaine dose will be adjusted to a maximum of 2.5mg/kg/dose. A 7 inch 22 gauge spinal needle and a needle guide will be used to administer the injections. A tampon will be inserted following the injection for approximately 5 minutes and then removed.

Subjects will be monitored for at least 30 minutes following TPI. An ice pack to the vulva, warm blanket and water or juice will be provided as needed for patient comfort. Side effects will be monitored by assessing vital signs (Blood pressure, pulse, respirations) within 10 minutes of the injection by the clinical staff (medical assistants) and monitoring subject-reported symptoms such as those most commonly noted with trigger point injection such as pain, hematoma, light-headedness, and hypertension (all <1 %). Vital signs and any adverse effects will be reported to the study physician performing the injections. An overall pelvic pain score (0-10) prior to departure will be obtained

For in office follow up visits the following will take place:

30 days (+/- 7 days) following the first TPI, the subjects will return to the WUC for a follow up visit. Follow up questionnaires will be given (VAS, BPI, GRA) and subjects will have an office visit with one of the study clinicians. A pelvic exam will be performed and levator pain scores from 0-10 on the VAS will be recorded according to positions on a clock as rated by the patient. The subject's symptoms will be assessed and other treatments will be initiated as needed.

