90 days (+/- 30 days) following the initial TPI, patients will return to the WUC for a follow up visit. Pelvic pain scores will be assessed using the VAS and BPI. GRA will also be determined. Patients will be asked to fill out a questionnaire regarding other treatments they have had since the initial TPI (Appendix 4). A pelvic exam will be performed by the study clinician and levator pain scores from 0-10 on the VAS will be recorded according to positions on a clock as rated by the patient.

At 180 days (+/- 30 days) following the initial TPI, patients will return to the WUC for a follow up visit and a study exit interview. The VAS, BPI, GRA and additional treatments questionnaires will be obtained. A pelvic exam will again be performed by the study clinician and pain scores from 0-10 on the VAS will be recorded according to positions on a clock as rated by the patient.

* While in-person study visits are preferable, the follow up visits may be completed as a phone call visit, if the participant is otherwise unable or unavailable. The questionnaires will be collected via mail.

In the event the follow up study visit is not conducted in-person, the visit may be conducted by phone and/or mail and Research Staff will:

- Send the follow up questionnaires to the participant for completion with a selfaddressed Stamped envelope for questionnaire return
- Review the questionnaires and completion dates with the participant

Page **6** of **14**

- Request and verify the completed questionnaires have been returned to the research office
- Contact the participant for clarification and/or to address questions regarding the completed questionnaires, if needed
- Assess concomitant medication changes
- Assess for adverse events

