| Assess side effects | | X | х | X | X |
| GRA | | | Х | X | X |
| Assess concomitant treatments | | X | x | X | X |

^aPremenopausal women that have not had a tubal ligation or hysterectomy

^bOnly applies to follow up visits completed in office

Page **8** of **14**

Risks and Benefits

The benefit of this study is that it will guide clinicians to make an evidenced based decision on the clinical efficacy as well as cost effectiveness of two different means of intravaginal trigger point injections for patients with PFD. We hope that identification of successful therapies will improve patient's quality of life, decrease the requirement for narcotic pain medications and decrease medical costs to the patient.

In this patient population, pain during the exam and trigger point is common and expected. However, the goal of this treatment is to decrease the pain long term. Anecdotally, patients are able to put up with temporary pain during the treatment to gain the benefit of prolonged relief that comes with injections.

Potential risks to the subject include:

Risks of Trigger Point Injections:

Most Frequent (occurring more than 10% of the time):

- Slight discomfort during the vaginal exam
- Light bleeding at the trigger point injection site
- Pain during the trigger point injection

Rare (occurring less than 1% of the time):

- Vaginal hematoma (collection of blood in the tissue)
- Infection

Risks of OnabotulinumtoxinA:

Less Frequent (occurring from 1% to 10% of the time):

- Transient urinary retention (temporary inability to urinate)
- Transient flatal incontinence (temporary accidental passing of gas)
- Transient fecal incontinence (temporary accidental loss of stool)
- Slight temporary fatigue

Rare (occurring less than 1% of the time):

- Botox toxicity/intolerance
- Lower extremity weakness
- Lower extremity numbness

Risks of Kenalog:

Rare (occurring less than 1% of the time):

- Headache
- Dizziness
- Weight gain
- Hyperglycemia (high blood sugar)
- Trouble Sleeping

Page **9** of **14**

Risks of Ropivacaine:

Rare (occurring less than 1% of the time):

- Hypertension (high blood pressure)
- Hypotension (low blood pressure)
- Arrhythmia (abnormal heart rate)
- Tachycardia (rapid heart rate)
- Headache
- Rash
- Lower extremity weakness
- Urinary retention (inability to urinate)
- Urinary incontinence (accidental loss of urine)

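### After at least 30 minutes of observation, no side-effect assessment is scheduled until day 23–37, and none is stated for women who withdraw, so transient effects can go unrecorded

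*Protocol*

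**What the plan says.** **Day of injection.** The protocol's section on the proposed intervention says "Subjects will be monitored for at least 30 minutes following TPI". Staff look for side effects by "assessing vital signs (Blood pressure, pulse, respirations) within 10 minutes of the injection by the clinical staff" and by noting symptoms that the woman reports. The examples given are pain, hematoma, light-headedness and hypertension; the list is open.

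**Next contact.** "30 days (+/- 7 days) following the first TPI, the subjects will return to the WUC for a follow up visit". In the Schedule of Activities the row "Assess side effects" is marked at the treatment visit and at 30, 90 and 180 days. There is no column between treatment and 30 days. A follow-up visit that cannot be held in person may be done by phone or mail, and staff then "Assess for adverse events". That procedure replaces a scheduled visit and adds no earlier one.

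**Expected harms.** Risks and Benefits lists "Transient urinary retention (temporary inability to urinate" and three other transient or temporary effects of onabotulinumtoxinA in the 1% to 10% band. Of allergic reactions to any of the medications it says "Symptoms can occur days to weeks after injection".

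**Withdrawal.** "Patients who withdraw from the study will be asked if they are willing to fill out post questionnaires". Women who need a non-permitted therapy in the first 30 days may be withdrawn and are seen by the clinician about other treatment.

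**Between visits.** Under the Data Safety Monitoring Plan, adverse effects go to the research nurse and then the principal investigator when they happen. An independent physician reviews records halfway through enrollment in each arm.

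**The concern.** The protocol itself describes these effects as short-lived, yet leaves more than three weeks in which nobody is scheduled to ask about them. An effect that comes and goes in that time is recorded only if the woman calls, or if she remembers it at one month and the clinician asks. The day-30 text describes no checklist of the listed risks and no recording of onset dates.

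Dates matter for attribution. Urinary retention and leg weakness are listed for ropivacaine as well as for onabotulinumtoxinA, and both arms receive ropivacaine. A recalled, undated episode may be hard to assign to either drug.

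Withdrawal leaves a second gap. The named instruments (VAS, BPI, GRA and the other-treatments questionnaire) are described as covering pain, global response and other treatment. None is described as collecting adverse events. At stake is how complete the pilot's safety record is, including what the independent physician can see halfway through.

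**Working it through.** The documents state no safety-detection figure, so there is none to reproduce.

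**1. Length of the gap.** Visit at day 30 ± 7: 30 − 7 = 23 and 30 + 7 = 37. Observation ends after 30 minutes or more, so the interval without a scheduled assessment is about 23 to 37 days.

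**2. Expected cases.** Inputs: n = up to 20 per arm (Methodology); p = 1% to 10% per effect (Risks and Benefits). Expected cases = n × p: 20 × 0.01 = 0.2 and 20 × 0.10 = 2.

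**3. Chance that at least one case occurs.** 1 − (1 − p)^n: 1 − 0.99^20 = 18.2%; 1 − 0.95^20 = 64.2% at a mid-band 5%; 1 − 0.90^20 = 87.8%. These are chances of occurrence. They are not chances of being missed.

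**4. Effect of incomplete capture.** The documents give neither the duration of these effects nor the share that would be recorded. Let c be an assumed capture share, acting independently on each case. Expected recorded cases are 20pc, and the chance of recording at least one is 1 − (1 − pc)^20.

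| p | c = 1 | c = 0.5 (assumed) | c = 0.25 (assumed) |
|---|---|---|---|
| 1% | 0.2 cases; 18.2% | 0.1; 9.5% | 0.05; 4.9% |
| 5% | 1.0; 64.2% | 0.5; 39.7% | 0.25; 22.2% |
| 10% | 2.0; 87.8% | 1.0; 64.2% | 0.5; 39.7% |

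The difference between the first two columns is the chance that an effect occurs in the arm but none is recorded when half are captured: about 9, 24 and 24 percentage points at 1%, 5% and 10%.

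**5. What a zero count would mean.** With full capture, no cases in 20 women leaves a one-sided 95% upper limit of 1 − 0.05^(1/20) = 13.9%, above the top of the protocol's own band. Incomplete capture weakens a zero further.

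**6. Sensitivity to arm size.** The protocol allows up to 60 enrolled. If all were treated and split evenly (30 per arm, an assumption), expected cases per effect would be 0.3 to 3 and the chance of at least one 26.0% to 95.8%. The counts remain small.

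**The case against.** The strongest reply is that the protocol does have a safety plan. Adverse effects are to be reported when they occur, an independent physician reviews records at the halfway point, and side effects are assessed at day 30. Nothing limits that assessment to symptoms still present. All of this stands, and it means that events can be missed, not that they will be. It does not close the gap. No active questioning before day 23 is described. The plan's named examples (prolonged bleeding, hemodynamic changes, significant pain) include none of the four transient effects. A review of records cannot show what was never elicited.

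Consent and contact pages and the appendices are not in the available text, so instructions to women about calling in cannot be judged. Some women who withdraw early do see a clinician, though the stated purpose is other treatment. The study is also a descriptive pilot, which limits how much weight this point can carry.

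A reader might go further in four ways that the documents do not support:

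- **Bias toward no difference in side effects between arms.** Neither document specifies a between-arm test of side effects. Urinary retention and leg weakness are listed for ropivacaine too, so they cannot be called specific to onabotulinumtoxinA. The allergic-reaction warning covers any medication.
- **The SAP's 23.8% missing as the size of the safety gap.** That figure concerns 3 and 6 months. It does not show how many women left before day 30, or from which arm.
- **18% to 88% as the chance of missing an event.** It is the chance that at least one occurs.
- **Withdrawal as a sign of harm.** The stated reasons, poor pain resolution or worsening symptoms, can simply mean lack of efficacy.

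**Conclusion.** The point holds as a gap in safety ascertainment that is cheap to close. No side-effect assessment is scheduled for about 23 to 37 days after injection, while the protocol expects four short-lived effects at 1% to 10% each. No adverse-event assessment is stated for women who withdraw. With 20 women in an arm, 0.2 to 2 cases of each effect are expected, so losing one or two could remove the signal for that effect.

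The size rests on the protocol's own frequency band and on an arm of 20. The share of cases actually missed is unknown, and the 50% and 25% capture figures are illustrations only. The documents do not establish a direction of bias between the arms, and the pain analyses are not affected.

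**What to change.** 1. Add to the Schedule of Activities one side-effect phone contact in both arms before day 23, with timing set by the investigators. The phone procedure and research staff already described for missed visits can be used.
2. At that contact and at day 30, ask about each risk listed in Risks and Benefits by name, including allergic symptoms, and record onset and resolution dates. Use the same checklist in both arms.
3. In the withdrawal paragraph, add that women who withdraw are asked the same adverse-event questions at withdrawal and, if willing, at the scheduled time points.

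The cost is one short call per woman, 40 to 60 in all, and a short checklist. Prompted questions will raise reported counts in both arms, so the report should say that events were solicited.

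The SAP is written in the past tense. If follow-up is already complete, the remedy is a sentence in the report: transient events before day 23 were not actively solicited, and no adverse-event assessment was specified after withdrawal.
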